9.7.2 Secondary analysis

Analysis of Participation rate

The following cases of total response and non-response will be identified and described for HCPs:

- Targeted HCPs: HCPs reached to whom an e-mail or e-mail has been sent or have been called
- Contacted HCPs: HCPs who have received the e-mail or have answered the phone call.
- HCPs who agreed to participate: HCPs willing to participate in the survey (e.g. by phone or by clicking on the link provided in the recruitment e-mail) or in the patient's recruitment
- HCPs with submitted questionnaire: HCPs who actually answered the questionnaire through the end and submitted it. (One or some missing answers are allowed across the questionnaire.)
- HCPs who recruited patients: HCPs with at least 1 patient having actually answered the questionnaire and submitted it by paper or web

For patients/caregivers, more simplified definitions will be calculated based on the following definitions:

- Contacted patients/caregivers: those who have been asked by HCPs to participate
- Patients/caregivers who agreed to participate: those who accepted the questionnaire
- Patients/caregivers with submitted questionnaire: those who actually answered the questionnaire and submitted it by paper or web

The participation rates of HCPs will be examined via the following ratios:

- Contact rate = Number of contacted HCPs divided by the total number of targeted HCPs
- Response rate = Number of HCPs who agreed to participate (in the survey or in recruitment of patients) divided by the total number of invited HCPs
- Cooperation rate = Number of HCPs with submitted questionnaire divided by the total number of HCPs who agreed to participate
- Refusal rate = (Number of contacted HCPs minus the number of HCPs who agreed to participate) divided by the total number of contacted HCPs

The participation rates will be presented by country and specialty.

The screening log which includes the HCPs' characteristics will enable to compare the participating and non-participating HCPs' profile to check if there is a selection bias.

Effect of EMs variations among targeted countries on success factors:

There could be variations between country affiliates of the MAH regarding the communication plan for EMs, including the route of distribution, target audience and layout or content of EMs as approved by national competent authorities. In order to take into account variations between member states concerning HCP specialties targeted, distribution routes and potential local adaptation to EMs, the success of EMs will be presented by country, distribution routes, version changes and HCPs targeted.”

Analysis of the differences between paper or web responding patients:

Differences in demographic characteristics, participation rate, completeness of reported data and success factors, between the paper and web respondents will be described.

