9.2.2.2 Exclusion criteria

HCP survey

The following exclusion criteria will be checked at the beginning of the web questionnaire:

- HCPs who are not involved in patient treatment
- HCPs who may have conflicts of interest with the survey (i.e. HCPs employed by regulatory bodies, pharmaceutical industries)
- HCPs who have participated in the previous waves of the survey
- HCPs who have already 2 or more colleagues participating in the survey from the same practice in the same wave

Patient survey

The following exclusion criteria will be checked at the beginning of the web questionnaire:

- Patients (or caregivers) who may have conflicts of interest with the survey
- Patients (or caregivers) who have participated in the previous waves of the survey

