9.9 LIMITATIONS OF THE RESEARCH METHODS

1. Selection bias

The potential for selection bias of HCPs participating in a survey is an inherent bias/limitation to any study based on volunteer participation. In order to quantify any selection bias, the distribution of each stratification criterion of HCPs (country, specialty, and the other available characteristics present in the screening log) will be compared between participants and non-participants.

There is also a potential selection bias related to patient participation in the survey. The patient selection is susceptible to cluster sampling bias. In addition, if a bias occurs in the selection of HCPs, the sample of patients will be skewed. Because the characteristics of the general SULIQUA patient population are not available, it is impossible to compare patients surveyed in the study to those general SULIQUA patients.

2. Limits inherent to web surveys

In such surveys, the generalisation and external validity of the results is restricted to HCPs who have an active e-mail address and are willing (and able) to answer a questionnaire online. These HCPs may not be fully representative of the whole targeted population (7) (8).

Among non-response bias, targeted HCPs may also have activated filters in their mail box in order to block spams and unsolicited e-mails. They may not even see the invitation to participate in the survey if a very strict degree of message filtering is set. Having multiple e-mail addresses could also be a critical situation. If the one used is not the primary address or if the HCPs do not check their e-mail box frequently, they will not receive the invitation during the recruitment period. Some HCPs who were sent a letter may not have received it. To overcome these potential limitations, HCPs will also be contacted by phone.

3. Limits inherent to paper questionnaires

Patient-reported outcomes are in general equivalent for both paper- and computer-collected questionnaires (9). However, data record and entry errors may occur when paper questionnaires are used. Such errors can be avoided when an electronic device is used for data collection (10). In this study, the paper-based option is provided because previous reports indicate that patients may prefer paper questionnaires (11).

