Annex 2 HCP survey questionnaire

**SURVEY TO EVALUATE THE KNOWLEDGE AND UNDERSTANDING OF THE KEY
SAFETY MESSAGES IN THE HEALTHCARE PROFESSIONAL GUIDE AND THE
PATIENT GUIDE FOR SULIQUA**

- HCP questionnaire -

SURVEY TO EVALUATE THE KNOWLEDGE AND UNDERSTANDING OF THE KEY SAFETY MESSAGES IN THE HEALTHCARE PROFESSIONAL GUIDE AND THE PATIENT GUIDE FOR SULIQUA

Section 1: Screener

S1. Are you currently employed by a pharmaceutical company or contracted by regulatory bodies (e.g. EMA = ZVA, Hungary = OGYEI, Italy = AIFA, Czech Rep =SUKL, Slovenia =JAZMP)?

1	No	()
2	Yes	()

Data: single punch

If S1=2 then THANK&CLOSE

S2. Have you ever prescribed / dispensed Suliqua?

1	Yes	()
2	No	()

Data: single punch

If S2=2 then THANK&CLOSE

S3. Approximately how many patients have you treated with /delivered Suliqua in the last 3 months?

.....

Data: Open numeric 0-500

If 0 => STOP then THANK&CLOSE

If >0 => continue

Section 2: HCP Practice information

D1. For how many years have you been working with patients with diabetes?

1	≤ 5 years	()
2	6 to 10 years	()
3	> 10 years	()

Data: single punch

D2a. What is your main medical specialty?

1	General practice (GP)/ family physician	()
2	Endocrinology/ Diabetology (Medical doctors or nurse practitioners)	()
3	Pharmacist	()
4	Internist	()
5	Gastroenterologist	
6	Geriatrics	
7	Other	()

Data: single punch

If D2=7 then THANK&CLOSE

(For UK questionnaires: Replace " Internist" by "Internal Medicine"; remove Gastroenterologists in UK as they do not prescribe antidiabetic drugs)

D2b. For how long have you been working in this specialty?

For |_|_| years

Data: open numeric, 2 digits

D3. In which type of setting do you work in? (you can select more than one answer)

1	Office	()
2	Hospital	()
3	Diabetes care clinic	()
4	Community Pharmacy	()
5	Hospital Pharmacy	()

Data: multiple punch

If D2a = 1,2,4,5 then ask i1,i2,i3

If D2a = 3 then ask i4,i5

(For UK: in the UK the term "Office" is not used: would rephrase to "Private Practice")

Section 3: Prescribing conditions and safety information/warnings of Suliqua 10-40 or 30-60 pen

Explanatory text

Please answer the following general questions about the prescribing conditions and safety information of Suliqua

Q1. Which educational materials (EM) related to Suliqua have you received ?

1	Guide for Healthcare professionals	 Yes  No  I do not remember

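### The cooperation rate in Section 9.7.2 mixes drop-out with HCPs screened out after agreeing and with HCPs who agreed only to recruit patients

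*Protocol*

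**What the plan says.** Protocol Section 9.7.2 lists the response and non-response cases for HCPs and fixes four participation ratios, to be shown by country and specialty. The ratio at issue is "Cooperation rate = Number of HCPs with submitted questionnaire divided by the total number of HCPs who agreed to participate".

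- **Denominator.** Agreement can be shown by phone or "by clicking on the link provided in the recruitment e-mail". Agreement to help with patient recruitment also counts. The response-rate definition confirms this: "Number of HCPs who agreed to participate (in the survey or in recruitment of patients) divided by the total number of invited HCPs".
- **Numerator.** It holds only "HCPs who actually answered the questionnaire through the end and submitted it".
- **Timing of the eligibility check.** Section 9.2.2.2 states for the HCP survey: "The following exclusion criteria will be checked at the beginning of the web questionnaire". In Annex 2 the form closes for HCPs employed by industry or contracted by regulators (S1), for those who never prescribed or dispensed SULIQUA (S2, "If S2=2 then THANK&CLOSE"), for those with no SULIQUA patient in the last 3 months (S3), and for specialty 'Other' (D2a).
- **Sampling frame.** Section 9.2.4.1 draws from OneKey lists stratified by country and specialty. It speaks of dividing eligible HCPs into strata, but describes no check of SULIQUA use before the draw.
- **Selection-bias check.** Section 9.9 says that HCP characteristics "will be compared between participants and non-participants". Section 9.7.2 and the abstract describe the same check in slightly different terms. None of the three defines the comparison group.

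The list of cases in 9.7.2 has no entry for an HCP found to be ineligible.

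**The concern.** A cooperation rate is read as the share of willing respondents who finished. Here two groups enter the denominator with no way into the numerator. The first is HCPs who agreed and were then closed by the screener. The second is any HCPs who agreed only to hand out patient kits and were never asked for an HCP questionnaire. Neither group has dropped out.

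Screen-outs are foreseeable. The frame does not select on SULIQUA use, and the rationale for Amendment 02 says uptake in the EU has been well below projection. The screened-out share should also vary between strata, because SULIQUA use will differ by country and specialty. D2a adds to this. Nurses are a target group, but the item names only nurse practitioners in endocrinology/diabetology, which leaves a nurse in another field with 'Other' and a closed form.

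At stake is the reading of the participation table. A stratum with many non-users would look uncooperative although its eligible HCPs finished as often as elsewhere. Because the comparison group in the selection-bias check is undefined, it is also unclear where the screened-out HCPs are placed there.

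**Working it through.** **The plan's own figures.** The protocol states no expected cooperation rate, so there is none to reproduce. The HCP sample size, which supplies the number submitted per wave, does reproduce:

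- 0.5 × 0.5 × 1.96² / 0.05² = 384.1 (stated 384)
- half-width at 128 per wave: 1.96 × √(0.25/128) = 8.66% (stated 8.66%)
- 384/0.85 = 451.8 (stated about 450) and 128/0.85 = 150.6 (stated 150)

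**Order of events.** In 9.7.2 the click on the recruitment e-mail is itself agreement. In 9.6.1 the HCP agrees first and then receives the link. Either way, agreement comes before the screener.

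**Formula.** Let S = 150 submitted per wave, c = completion among eligible HCPs who agreed to the HCP survey, i = screened-out share of all who agreed, and k = share who agreed only to patient recruitment.

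- Eligible survey-agreers = S/c
- All who agreed = (S/c)/(1 − i − k)
- Written cooperation rate = S divided by all who agreed = c(1 − i − k)
- Rate with both groups removed = c

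The documents give no value for c, i or k. The values below are assumptions.

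**Results at c = 85%, k = 0.** Eligible survey-agreers are 150/0.85 = 176, so true drop-outs are 26 in every row.

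| Screened out (i) | All who agreed | Written rate | Rate among eligible | Drop-outs as share of agreed but not submitted |
|---|---|---|---|---|
| 0% | 176 | 85.0% | 85% | 100% |
| 10% | 196 | 76.5% | 85% | 57% |
| 30% | 252 | 59.5% | 85% | 26% |
| 50% | 353 | 42.5% | 85% | 13% |
| 70% | 588 | 25.5% | 85% | 6% |

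With i = 30% and k = 10% the written rate is 0.85 × 0.60 = 51%.

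**Sensitivity to c (k = 0).** The last column depends strongly on c. At c = 70% it is 73% when i = 10% and 41% when i = 30%. At c = 95% it is 31% and 10%.

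**Between strata.** Take two strata that both have c = 85%, one with i = 10% and one with i = 50%. They would report 76.5% and 42.5%, a gap of 34 points with no difference in drop-out.

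**Selection-bias check.** Section 9.2.4.1 expects about ten HCPs contacted per analysable questionnaire: 128 × 10 = 1,280 contacted, of whom 1,280 − 150 = 1,130 do not submit. At c = 85% and k = 0, the screened-out HCPs number 20, 76, 176 and 412 for i = 10%, 30%, 50% and 70%. As a share of 1,130 that is about 2%, 7%, 16% and 36%. Drop-outs are 26, or about 2%. The rest, about 96%, 91%, 82% and 61%, are refusers or unreachable HCPs whose eligibility is unknown.

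**The case against.** The strongest reply is that this is a descriptive secondary rate. It feeds neither the three success factors, nor the 80% rule, nor the sample size. The weights come from the HCP population distribution, not from participation. All of that stands and limits the weight of the point.

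It can also be said that Section 9.7 leaves detail to a statistical analysis plan. That holds for the coding of the selection-bias comparison, but not for the rate. Section 9.7.2 fixes the cases and the formula, and an analysis plan that follows them reproduces the problem.

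Three stronger readings are tempting, and the documents do not support them:

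- **That the rate measures ineligibility rather than drop-out.** It mixes the two, and which dominates depends on shares the protocol does not give. With 10% screened out and completion of 70% to 85%, drop-out is still the larger part. Section 9.6.1 has the survey's background and objectives explained at invitation, so some non-users may decline before they count as having agreed.
- **That the selection-bias check becomes a contrast of users with non-users because screened-out HCPs sit among the non-participants.** The group is undefined, so placing them there is an inference. An HCP who only recruits patients could as well count as participating. In most of the scenarios above, screen-outs are a small part of those who did not submit. Removing them would not fully cure the comparison, because HCPs of unknown eligibility still include non-users.
- **That everyone who distributes kits inflates the denominator.** The offer in Annex 2 comes at the end of the HCP questionnaire, so HCPs recruited that way enter the numerator once they submit. Only HCPs selected separately for patient recruitment under Section 9.1 can be recruitment-only. Their number is unknown, and theirs is a different task, not ineligibility.

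**Conclusion.** The point stands as a defect in a fixed definition. By the protocol's own wording, screened-out HCPs and any recruitment-only HCPs are in the cooperation-rate denominator and cannot be in its numerator. The reported rate is c(1 − i − k) where the reader will take it as c.

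The direction is certain: the rate can only be pulled down. The size is not, because it rests on assumed shares. At c = 85% and k = 0, the loss is 8.5 points with 10% screened out, 25.5 points with 30% and 42.5 points with 50%. The practical harm is greatest in the table by country and specialty, where differences in SULIQUA use would look like differences in cooperation.

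For the selection-bias check the supported statement is narrower: the comparison group is undefined and should be defined. No conclusion on the effectiveness of the educational materials changes, and the sample size is unaffected.

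**What to change.** In Section 9.7.2:

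1. Add the case 'screened out / ineligible (S1–S3, D2a)'.
2. Count agreement to the HCP survey separately from agreement to patient recruitment, and report the latter as its own rate.
3. Define cooperation rate = submitted HCP questionnaires / (HCPs who agreed to the HCP survey − those screened out).
4. Define the comparison group for the selection-bias check, with the same terms in the abstract, 9.7.2 and 9.9. Show known-ineligible HCPs apart from eligible break-offs, and both apart from refusers and unreachable HCPs of unknown eligibility. State that this last group still contains non-users.

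The cost is a text change and one disposition code in the contact log. The questionnaire routing already identifies the item that closed the form, so nothing new is asked of HCPs. One practical point needs care: Section 9.2.3 has unsubmitted web questionnaires destroyed, so the closing item must be written to the log first. For Wave 1, already in the field, the corrected rate depends on whether that item was kept. If it was not, the Wave 1 report should say that its rate includes screened-out HCPs.

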9.7.3 Interim analysis

Two interim and 1 final analysis corresponding to 3 waves of survey will be performed (Section 6).

9.8 QUALITY CONTROL

9.8.1 Data collection, validation and data quality control at IQVIA level

Data will be collected using a web or paper questionnaire.

The survey will be conducted according to the Standard Operating Procedures (SOPs) of IQVIA Primary Intelligence and IQVIA Real World Evidence Solutions.

For web version of the questionnaires, data will be collected using an electronic data capture system developed following a full validation process. A rigorous System Development Life Cycle (SDLC) is used for validation that complies with internal IT SOPs of Primary Intelligence (IQVIA). Unit testing and formal validation occur on all appropriate systems and components during the build stage. The SDLC is fortified with SOPs addressing validation for all clinical and risk management-related applications. The internet-based repository will be used to store survey data and, other relevant program information. Questions are programmed to ensure that they are asked in the appropriate sequence. Skip patterns are clearly indicated. Respondents cannot go back to a question once the question has been answered and they cannot skip ahead. Response options presented in a list are randomized to minimise positional bias. Programming will be reviewed by quality control and simulated users (User Testing) prior to implementation.

For the paper questionnaire, respondents will be asked to complete questionnaire thoroughly with a ball-point pen and will be informed that responses modified (deletion, overprint) by participants will be considered as missing. Questions will be ordered in a way that no response to one question is available later in the questionnaire. The questionnaire will use multiple visual elements together to improve skip pattern compliance.

Collected data will be entered and stored in a database specific to the survey and the country. A study database will be created by the merging of databases of each country. HCP identifying information will be stored separately from survey data.

Data will be checked in terms of consistency before data analysis:

- Removal of duplicates (if required)
- Data labelling and data formatting
- Range and consistency checks for each variable to identify potential non admissible values
- Cross-check the consistency of data for related variables (if feasible)

The study database will be locked once validated.

9.8.2 Data quality control at site level

Not applicable

9.8.3 Approaches for validating the questionnaires

Both the HCPs and patient questionnaires will be user tested for their comprehensibility, consistency and the appropriateness of terms used (Section 9.4). The questionnaires will be translated from English into local language using the back and forth method to ensure an accurate translation of the local versions of the questionnaire will be validated by the MAH. Translation and back translation will be performed by IQVIA Primary Intelligence personnel.

9.8.4 Approaches for validating the results

The quality control for validating the results will be conducted at 5 levels:

1. At IQVIA Primary Intelligence management level, every effort will be undertaken to collect complete and validate data:
 - Verification of the reliability and security of the web questionnaire interface by a qualified web-master for each country
 - Validation of the quality of data entry for a random sample of $\sqrt{n + 1}$ of the total paper questionnaires will be performed by a qualified data manager according to a Data Validation Plan
 - Monitoring of the quality and datasets definition by a qualified data manager. In the background of the web questionnaire, real-time checks of the answers provided by the respondents will be developed. Non admissible answers (i.e. incorrect or unusual values, outlying values) will be detected and queries sent to the HCP
2. At the study database level (after merging datasets of each country), final data quality checks will be applied (beyond the data management process):
 - Distribution of each variable in order to count the number of missing values and estimate the associated relative percentage,

- Identification and count of non-analysable questionnaires
- Estimation of the percentage of non-submitted questionnaires

Any changes in the database will be tracked and documented. The country-datasets will be stored in a dedicated database. Once the data is validated and quality checked, the database will be locked.

3. At the statistical analysis level: all data management and statistical analysis programs developed and used in the analysis will be documented and quality checked. All versions generated will be dated, kept with accompanying documentation and archived. The original database will be stored. A derived database will be created for the new versions of the data, in order to include recoding and computing of new variables, especially stratification of continuous variables, combination of modalities for categorical variables, calculation of composite indicators, etc.
4. At the results level, a data review will be done to ensure data integrity. A statistical analysis report including all the results will be provided for review and discussion. The final statistical report will take into account the reviewers' comments.
5. At the study level, all aspects of the study will be conducted according to the SOPs of IQVIA Real World Evidence Solutions and Primary Intelligence divisions.

The study documents have been approved by people competent in medical and safety areas of IQVIA. According to the SOPs, an independent review of the survey results and report will be conducted by a person who was not in charge of their preparation.

9.8.5 Safeguards, security and traceability of contacts

Operators of the call centre specialised in health surveys, will be assigned to the project and trained on the survey methodology prior to fieldwork. The e-mails contacts and phone calls will be traced using the management software. All survey aspects from protocol development to the reporting of the results will be conducted according to the SOPs of IQVIA Real World Evidence Solutions and Primary Intelligence divisions. These SOPs can be consulted on site (6).

